#### **Procedure history**

Prior medical procedures or surgeries are not to be summarized and are only provided in a by-participant data listing based on the ES.

### **6.1.4 Prior/concomitant/follow-up medications**

Tabulations will be presented for prior and concomitant medications separately which the details are listed below:

#### **Prior and concomitant medications**

Medications are categorized as follow:

- Prior medication
  - Prior medications include any medications that started prior to date of the first dose of BRV.
- Concomitant medication
  - starts before first dose of IMP and is ongoing at day of first dose of IMP
  - starts on or after first dose of IMP

A listing of prior and concomitant medications, which includes the reported term, the anatomical therapeutic chemical subgroup (level 1 and 3) in WHO-DRL, is provided.

#### **Concomitant medical procedures**

Concomitant medical procedures or surgeries are not to be summarized and are only provided in a by-participant data listing based on the ES.

## 6.1.5 Data derivation rules

### 6.1.5.1 Handling of dropouts or missing data

Participants who drop out from the study before completion of study procedures and for any other reason than for safety issues can be replaced with participants of the same gender after consultation with the sponsor.

In general, there will be no imputation of missing data unless otherwise stated below. Handling of missing data for PK results is described in Section 5.7.1.1. Safety laboratory data will be handled as described in Section 5.6.

#### 6.1.5.1.1 Incomplete dates and times

Partial dates may be imputed for the following reasons:

- Classification of AEs as treatment-emergent
- Classification of medications as prior or concomitant

Imputed dates will not be shown in the listings; all dates will be displayed as reported in the database.

The following rules will be applied for partial start dates and time:

- If only the month and year are specified and the month and year of the first dose of IMP is not the same as the month and year of the start date, then use the 1st of the month, or the date of Screening if this is later (if the latter imputation results in an end date that is earlier than the start date, then use the 1st of the month). If time is missing this will be imputed as 00:00 h
- If only the month and year are specified and the month and year of the first dose of IMP is the same as the month and year of the start date, then use the date of the first dose of IMP. If this results in an imputed start date that is after the specified end date, then use the 1st of the month, or the date of Screening if this is later (if the latter imputation results in an end date that is earlier than the start date, then use the 1st of the month). If the imputed date is the date of dosing then time will be imputed as the start time of the dosing (ie, event will be regarded as treatment-emergent)
- If only the year is specified, and the year of the first dose of IMP is not the same as the year of the start date then January 01 will be used. If time is missing this will be imputed as 00:00 h
- If only the year is specified, and the year of the first dose of IMP is the same as the year of the start date, then the date of the first dose of IMP will be used. If this results in an imputed start date that is after the specified end date, then January 01, or the date of screening if this is later will be used (if the latter imputation results in an end date that is earlier than the start date, then January 01 will be used). If the imputed date is the date of first dose of IMP then time will be imputed as the start time of the study medication intake (ie, event will be regarded as treatment-emergent)
- If the start date is completely unknown, then use the date of dosing. If this results in an imputed start date that is after the specified end date, then use January 01 of the year of the end date, or the date of Screening if this is later.

The following rules will be applied for partial stop dates:

- If only the month and year are specified, then use the last day of the month

- If only the year is specified, then use December 31 of the known year
- If the stop date is completely unknown, do not impute the stop date

Missing or partially missing dates and/or times will be imputed as described in Table [below](#). AE duration is computed and reported in day and time format: xx d hh:mm. Duration is not calculated when the outcome date is missing.

**Table 5–1: Calculation rules for duration of adverse events**

Data availability	Onset date/time	Outcome date/time	Calculation rules
Complete data	D1/T1	D2/T2	Duration = $[(D2 - D1)*24 + (T2 - T1)]/24$ d
End time missing	D1/T1	D2/--	End time is substituted by time 23:59h (=23.98 in decimal format) Duration = $<[(D2 - D1)*24 + (23.98 - T1)]/24$ d
Start time missing	D1/--	D2/T2	If D1 is the same date as the date of first dose of IMP, Onset time is substituted by the start time of dosing ( $T_{dose}$ ). Duration = $<[(D2 - D1)*24 + (T2 - T_{dose})]/24$ d Otherwise the onset time is substituted by time 00:00h Duration = $<[(D2 - D1)*24 + (T2)]/24$ d
Start and end time missing	D1/--	D2/--	Duration = $<D2 - D1 + 1$
Start day and time missing	--/--	D2/T2	Duration = $[(D2 - D0)*24 + (T2 - T0)]/24$ d For a participant in the SS, D0 and T0 are the date and time of first administration of study medication and for screen failures, D0 is the date of the screening visit and T0 = 00:00h
End day and time missing	D1/T1	--/--	If the stop date and time are missing, duration will not be calculated.
Start and end date missing	--/--	--/--	If the stop date and time are missing, duration will not be calculated.

SS=Safety Set.

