## **10 ASSESSMENT OF SAFETY**

### **10.1 Adverse events**

#### **10.1.1 Definitions**

##### **10.1.1.1 Adverse event**

An AE is any untoward medical occurrence in a patient or clinical investigation subject administered a pharmaceutical product that does not necessarily have a causal relationship with this treatment. An AE can therefore be any unfavorable and unintended sign (including an abnormal laboratory finding), symptom, or disease temporally associated with the use of a medicinal (investigational) product, whether or not related to the medicinal (investigational) product.

In order to ensure complete safety data collection, all AEs occurring during the study (ie, after the signing of the Informed Consent form), including any pretreatment and posttreatment periods required by the protocol, must be reported in the eCRF even if no IMP was taken but specific study procedures were conducted. This includes all AEs not present prior to the initial visit and all AEs that recurred or worsened after the initial visit.

Signs or symptoms of the condition/disease for which the IMP is being studied should be recorded as AEs only if their nature changes considerably or their frequency or intensity increases in a clinically significant manner as compared to the clinical profile known to the Investigator from the subject's history.

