In summaries including relationship, the following relationships will be summarized: ‘Not related’, ‘Related’. Participants who experience the same event multiple times will be included in the most related category for tabulations by maximum relationship. Events with missing relationship will be considered as ‘Related’ for summary purpose but recorded as missing in the listings.

In summaries including intensity, the following intensity categories will be summarized: ‘Mild’, ‘Moderate’, ‘Severe’. Participants who experience the same event multiple times will be included in the most severe category for tabulations by maximum intensity. Events with missing intensity will be considered as ‘Severe’ events for summary purposes but recorded as missing in the listings.

Adverse event summaries will be ordered alphabetically by SOC and decreasing frequency of PT within SOC.

A listing for all AEs will be presented by participant and will include the onset date/time and outcome date/time of the event (including relative days), the AE duration (derived), pattern of event, intensity, relationship, action taken and outcome.

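### The adverse event duration rules give negative durations for events that ended before the first dose, and a date-only check can class an event over before dosing on Day 1 as treatment-emergent

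*SAP*

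**What the plan says.** SAP Table 5–1 (duration rules for adverse events) contains two relevant rows.

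- **Start day and time missing, end known.** The duration is the time from D0/T0 to the recorded end D2/T2. For dosed participants the anchor is fixed: "For a participant in the SS, D0 and T0 are the date and time of first administration of study medication". For the others it differs: "for screen failures, D0 is the date of the screening visit and T0 = 00:00h".
- **Start time missing, start date known.** "If D1 is the same date as the date of first dose of IMP, Onset time is substituted by the start time of dosing". On any other date the onset time becomes 00:00h.

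The text just before the table in SAP 6.1.5.1.1 reads: "Missing or partially missing dates and/or times will be imputed as described in Table".

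The same section has a separate list of rules for partial start dates. Its stated purposes are to classify events as treatment-emergent and medications as prior or concomitant. A completely unknown start is first set to the dosing date, with a fallback: "If this results in an imputed start date that is after the specified end date, then use January 01 of the year". The year meant is the one in which the event ended, and the Screening date takes over if it is later. When only the month and year, or only the year, are known and match the first dose, the onset becomes the dosing date. The time becomes the dosing time, and the event is declared treatment-emergent. These rules also have a fallback, triggered when the imputed start date is later than the end date.

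Protocol 10.1.1.1 collects events from informed consent. SAP 5.6.2 lists all of them by participant, with a derived duration.

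**The concern.** An event that resolved before the first dose cannot have started at the first dose. The start-missing row assumes that it did, for every dosed participant. It lacks the fallback that 6.1.5.1.1 applies to the same unknown start, although the row already uses the screening visit for screen failures. The result is an impossible value. It would also be listed as exact, because this row does not carry the upper-bound sign (<) that Table 5–1 puts on its other substituted-time rows.

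The partial-date rules matter more in principle because they feed the primary safety variable, the incidence of treatment-emergent events. Their fallback looks at calendar dates only. On Day 1, a recorded end time can precede the dose while the dates are equal. An event known to be over before dosing would then be counted as treatment-emergent, in an uncontrolled study of 12 participants.

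**Working it through.** **Inputs**

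- Duration formula (SAP Table 5–1, start day and time missing): [(D2 - D0) × 24 + (T2 - T0)]/24 days, with D0/T0 the first dose.
- Relative day (SAP 5.1.1.1.1): there is no Day 0, so Day -k is k days before Day 1.
- Screening: Day -28 to Day -2 (SAP 5.1.1.1.3). Confinement starts on Day -1, and events are recorded at Screening (Protocol 8.1).
- Participants: 12 (SAP 3).
- Dose time: not given. Assumed 08:00, varied from 07:00 to 10:00.

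The plan gives no figure of its own to reproduce.

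**Step 1: start day and time missing, end before the first dose**

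| Recorded end | Calculation | Duration (days) |
|---|---|---|
| Day -28, 12:00 | (-28 × 24 + 4)/24 | -27.83 |
| Day -20, 12:00 | (-20 × 24 + 4)/24 | -19.83 |
| Day -5, 12:00 | (-5 × 24 + 4)/24 | -4.83 |
| Day -2, 12:00 | (-2 × 24 + 4)/24 | -1.83 |
| Day 1, 06:00 | (0 - 2)/24 | -0.083 |

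For the Day -5 case, a 07:00 dose gives (-120 + 5)/24 = -4.79 and a 10:00 dose gives (-120 + 2)/24 = -4.92. The dose time changes the size and never the sign.

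**Step 2: Day 1 onset, time missing, end on Day 1 at 06:00**

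The onset is set to the dosing time, so the duration is (6 - 8)/24 = -0.083 days. For dose times from 07:00 to 10:00 it runs from -0.042 to -0.167 days. An onset at 00:00h would give 6/24 = +0.25 days.

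**Step 3: the 6.1.5.1.1 fallback applied to duration**

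Take an assumed dose on 10 March at 08:00, Screening on 20 February of the same non-leap year, and an event of unknown start that ended on 5 March (Day -5) at 12:00.

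- Table 5–1 gives -4.83 days.
- The fallback start is the later of 1 January and 20 February, so 20 February. From 00:00h that day to 5 March at 12:00 is 13 days and 12 hours, reported as <13.5 days.

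**Step 4: the partial-date rules and treatment-emergent status**

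Take an event with only the month and year of onset known, matching the first dose, and a recorded end on Day 1 at 06:00 with dosing at 08:00.

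1. The start date is imputed as Day 1.
2. The fallback needs a start date after the end date. Both are Day 1, so it does not trigger.
3. The time is imputed as 08:00, two hours after the recorded end, and the rule declares the event treatment-emergent.
4. Protocol 12.4.1 agrees, because it counts an onset at the moment of first dosing. SAP 5.6.2 requires onset later than the first dose, so read literally it does not.

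The year-only rule behaves the same way.

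**Step 5: size**

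One participant is 1/12 = 8.3 percentage points. This is a maximum: the shift occurs only if the participant has no other treatment-emergent event.

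**The case against.** **Consequence.** Derived duration is reported only in the by-participant listing. No summary or endpoint uses it, and a negative value is visible on its face. The data-cleaning checks (Protocol 11.3.2) and the Data Evaluation Meeting (Protocol 12.5) offer chances to query it. This stands and keeps the point small, although neither step is stated to catch it.

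**Likelihood.** The start-missing row needs an unknown start day together with a known end date and clock time. Poor recall during Screening would often lose the end time too, and Table 5–1 has no row for that case. The Day 1 cases need a recorded end time before dosing in an in-house participant with an incomplete onset. This also stands. Confinement does not remove the first case, because Screening lies outside the unit.

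**Stronger readings that the documents do not support.**

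- A reader might infer that every missing onset day gives a negative duration. Screen failures use the screening visit, no duration is calculated without an outcome date, and an end after the first dose gives a positive value.
- A reader might infer that the SAP gives one event two contradictory onsets. The partial-date list serves classification and Table 5–1 serves duration. Imputed dates are not shown in listings. What is missing is a safeguard in the table.
- A reader might infer that the Day 1 row of Table 5–1 itself makes a pre-dose event treatment-emergent. It is a duration rule. It reaches classification only if its substituted time is reused there. The sentence "Missing or partially missing dates and/or times will be imputed as described in Table" allows that reading, but the SAP does not state it, and the wording of SAP 5.6.2 would still exclude an onset exactly at dosing. The firmer route is the date-only check in Step 4.

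**Conclusion.** Wrong as written, with small impact. Two rows of Table 5–1 give a negative duration whenever they apply to a dosed participant's event with a recorded end before the first dose. The sign does not depend on the dose time. The effect is confined to the listing.

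The date-only check in the month-and-year and year-only rules of SAP 6.1.5.1.1 can class an event recorded as over before dosing on Day 1 as treatment-emergent. That conclusion rests on the rule's own statement and the protocol definition; the literal SAP 5.6.2 definition points the other way. The shift in incidence is at most 8.3 percentage points per misclassified participant with 12 dosed, and smaller if replacements enlarge the Safety Set. The pattern is rare, and the documents give no rate.

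**What to change.** **In Table 5–1:**

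- Start day and time missing, and the recorded outcome date/time before the first dose: replace D0/T0 with the fallback that 6.1.5.1.1 gives for an unknown start (January 01 of the end-date year, or the Screening date if later) at 00:00h. Report the duration as an upper bound (<). The bound assumes that the onset was no earlier than that anchor, so check it if Screening and outcome fall in different calendar years.
- Day 1 onset with the time missing, and the outcome before dosing: use 00:00h.

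**In 6.1.5.1.1**, add three statements:

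- The comparison of imputed start with end uses date and time wherever a time is recorded.
- No imputed onset may be later than the recorded outcome.
- An event with a recorded outcome before the first dose is pre-treatment.

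The last statement settles these cases whichever treatment-emergent definition is applied.

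**Cost:** a few sentences of SAP text and a small change to the adverse event derivation program. No protocol amendment, extra data or extra participants are needed. The downside is an upper-bound duration, not an exact one, for these few events.

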### 6.1.6 AEs of Special Interest

The AEs of special interest include:

- Autoimmune nephritis

- Nephritis
- Nephritis allergic
- Tubulointerstitial nephritis
- Tubulointerstitial nephritis and uveitis syndrome
- Potential Hy's Law, defined as  $\geq 3 \times \text{ULN}$  ALT or AST with coexisting  $\geq 2 \times \text{ULN}$  total bilirubin in the absence of  $\geq 2 \times \text{ULN}$  ALP, with no alternative explanation for the biochemical abnormality, must ALWAYS be reported to UCB as an AE of special interest (ie, without waiting for any additional etiologic investigations to have been concluded).

#### **6.1.7        Compliance**

A study participant is considered compliant with treatment if the participant takes the study IMP at all of 12 scheduled time points. Participants who do not take all 12 doses are to be considered non-compliant to treatment and are to be discussed at the DEM. A data listing for treatment compliance is not provided.

#### **6.2        Appendix 3: Changes to Protocol-Planned Analyses**

Not applicable.

